8.4 Reporting of Adverse Events and Serious Adverse Events

In order to assure prompt and complete reporting of adverse events or complications, all non-serious AEs occurring through the 3-month follow-up visit and all serious AEs occurring through the 12-month follow-up visit are recorded in the WebDCU™ system.

For each AE, the clinical site staff records the event in WebDCU™, providing relevant information such as the AE description, the dates of onset and resolution, severity, and seriousness. For SAEs, they also must provide the suspected relationship to stroke, suspected relationship to thrombolysis, suspected relationship to the study drug, and a narrative description of actions taken as a result of the SAE.

8.5 Review and Expedited Reporting of Serious Adverse Events

All serious AEs must be reported by the site into the WebDCU™ system within 24 hours of first knowledge of the SAE. Additionally, all current study data for that particular subject must be entered to allow for timely review by the MSMs. Upon entry of a serious AE, WebDCU™ triggers notification of the SAE to the Project Manager. The narrative section of the SAE report is reviewed by an AMM, and if the narrative is satisfactory the SAE is forwarded to the MSMs.

The MSMs conduct independent blinded reviews of all SAEs entered into WebDCU™. Should any medical reviewer need additional subject data to conduct his review, those data may be accessed on the WebDCU™. The MSMs submit their opinions on whether the AE was a) serious, b) unexpected, and c) related to the study drug within 72 hours of notification of the SAE. The MSMs may contact the site for more information or discussion. If two of the three parties involved with the

reporting and/or reviewing of the SAE (i.e., site investigator and either of the MSMs, both MSMs, or all three) believe the AE is serious, study drug-related (possibly, probably or definitely), and unexpected, the SAE is considered to require expedited reporting.

When it is confirmed that an event requires expedited reporting, the Project Manager contacts the site with instructions for completion of a MedWatch form, or other safety reporting forms. An electronic copy of the MedWatch form is sent through the WebDCU™ system and the site staff enters the required information. Following the site's completion of the MedWatch form, or other safety reporting form, SDCC submits the MedWatch form, or other safety reporting forms, to the FDA. SDCC also distributes this information to the DSMB (through the NINDS DSMB Liaison), Health Canada (through the Canadian Coordinating Center), and the clinical site PIs. Each clinical site PI is then responsible for reporting to his/her own IRB/REB.

[figure not shown]
8.6 Follow-Up Reporting of Serious Adverse Events

After the submission of the initial MedWatch report, or other safety report, the clinical site staff is responsible for obtaining any follow-up information about the SAE. All follow-up information should be actively sought by the clinical site and must be submitted to the SDCC as soon as the information becomes available. The SDCC distributes the follow-up MedWatch report, or other safety report, to all parties receiving the initial MedWatch report, or other safety report.

8.7 Additional Safety Review

A summary of all adverse events and a summary of all MedWatch reports, or other safety reports, submitted for the previous year will be included in the annual reports submitted to the FDA and Health Canada, and reports submitted to the DSMB. In addition, reports of all adverse events are submitted in aggregate to the DSMB on a regular basis.

ALIAS Study SAE Reporting and Monitoring Flowchart

8.8 Monitoring of Specific Adverse Events

Incidences of the following specific adverse events are monitored by the Trial EC in a blinded manner and by the unblinded Trial personnel and the DSMB by treatment group throughout the study:

- Neurological deterioration as assessed by the investigator of an increase of 4 points or more on the NIHSS anytime within 48 (\pm 6) hours of randomization
- Neurological death from stroke during hospitalization or within 7 days (\pm 6 hours) of randomization, whichever is shorter
- Recurrent stroke within 30 (\pm 7) days of randomization
- Atrial fibrillation within 48 (\pm 6) hours of randomization
- Severe or life threatening pulmonary edema or CHF within 48 (\pm 6) hours of randomization
- Shortness of breath within 48 (\pm 6) hours of randomization
- Symptomatic ICH within 24 (\pm 6) hours of randomization
- Asymptomatic ICH as assessed by the CT scan at 24 (\pm 6) hours
- Death from any cause within 30 (\pm 7) days of randomization
- Death from any cause within 90 (\pm 14) days of randomization

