Renal insufficiency. Renal insufficiency shall be defined as renal dysfunction, shown by a 20% increase in serum creatinine from baseline, not requiring renal replacement therapy.

Urinary tract infection (lower). Bacterial infection of the bladder, often as a complication of Foley catheter placement. Should be suspected based upon the presence of white cells and/or nitrites in the urine and proven by culture.

Respiratory failure. Hypoxemia or hypercarboxemia requiring mechanical ventilation (either intubation or non-invasive with BiPAP/CPAP).

Respiratory insufficiency. Hypoxemia or hypercarboxemia that can be managed without mechanical ventilation (either intubation or non-invasively with BiPAP/CPAP).

Acute treatment-emergent hypertension. Elevated blood pressure occurring in the first 48 hours of 220 systolic or 120 mmHg diastolic, OR an increase of 20% in either systolic blood pressure or mean arterial pressure over baseline values.

Increased intracranial pressure. Raised ICP (> 25 cm H₂O) requiring interventional treatment (e.g., hemicraniectomy, placement of an external ventricular drain).

Neurological deterioration. Any increase in NIH stroke scale of 4 points or more, over the baseline value, occurring at any point between randomization and 48 hours.

Stroke death. Death from stroke (neurological death attributed to the stroke) within 7 days (\pm 6 hours) or during hospitalization for the qualifying stroke.

Recurrent stroke. A new stroke occurring in a new vascular territory, separated in time from the initial stroke event by 48 hours or more.

Progression of stroke. Worsening of the same stroke symptoms that defined the initial stroke event, involving deficits attributable to the same vascular territory and occurring within 48 hours of the original stroke event.

Pneumonia. The following criteria define pneumonia:

- (i) hypoxemia ($S_aO_2 < 90\%$)
- (ii) pulmonary air space disease defined by clinical examination and/or chest X-ray
- (iii) fever (temperature $> 38^\circ C$)

Two of three are required. Cough, dyspnea, pleuritic chest pain and delirium are additional supportive symptoms/signs. Pneumonia is confirmed by culture of a single bacterial or viral organism or by clinical resolution of symptoms with antimicrobial treatment and absence of a good alternate diagnosis (e.g., pulmonary embolus, atelectasis, congestive heart failure).

Hypotension. Hypotension is defined as the syndrome of low blood pressure with SBP < 85 mmHg.

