10.2.3 Safety Outcomes

Several specific adverse events are monitored throughout the study (see Section 8.8). However, death from any cause within 30 (\pm 7) days of randomization is evaluated statistically during and at the end of the Trial. We propose to use the 30-day mortality as the primary safety outcome because of the observed differences between the treatment groups during that period in the Part 1 of

the ALIAS Trial. Furthermore, the causes of death during that period are suspected to be more related to the study treatment compared to deaths occurring post-30 days from randomization. Clearly, the seriousness of this event requires close monitoring; therefore, we plan to conduct frequent interim analyses of this outcome (see Section 10.7.2).

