10.7.2 Statistical Stopping Guidelines for Safety

Because of concerns about excess deaths in one group over the other in Part 1 of the ALIAS Trial, we have established one set of statistical safety stopping guidelines based on mortality within 30 days from randomization as shown in Table 10.7.2.

Table 10.7.2 Suggested approximate stopping guidelines for safety.

Approximate N at interim monitoring*	Total # death*	Maximum split in # of death between the two groups to yield LL of 99% CI on RR < 1.0		Unadjusted RR**	LL of 99% CI for the unadjusted RR
		Group A	Group B		
100	15	3	12	4.00	0.959
200	30	9	21	2.33	0.981
300	45	16	29	1.81	0.925
400	60	22	38	1.73	0.969
500	75	29	46	1.59	0.952
600	90	35	55	1.57	0.986
700	105	42	63	1.50	0.977
800	120	49	71	1.45	0.972
900	135	55	80	1.45	0.998
1000	150	62	88	1.42	0.994
1100	165	69	96	1.39	0.991

* Assumes 15% overall 30-day death rate.

** In practice, the RR will be estimated adjusting for thrombolysis treatment, age, and baseline NIHSS, and its LL of the 99% CI will be used for stopping criterion.

The above stopping guideline is based on the total number of deaths observed within 30 days. Hence, the first interim monitoring point occurs after a total of 15 deaths are observed, which should translate to when approximately 100 subjects have had the 30-day follow up, assuming a 15% overall 30-day death rate. The 3-to-12 split of the 15 deaths yields an unadjusted RR of 4.0 with the lower limit (LL) of its one-sided 99% CI at just below 1.0. The split that is more extreme (i.e., 2-to-13, 1-to-14, or 0-to-15) will yield an LL of greater than 1.0.

Subsequent interim monitoring point occurs after every additional 15 deaths (within 30 days) are observed.

Because thrombolysis treatment, age, and baseline NIHSS are strong prognostic indicators of death, in practice, we will estimate the RR adjusting for these covariates, and we would become alerted if the LL of its one-sided 99% CI begins to approach 1.0. The DSMB will evaluate this and other pertinent data to consider stopping the trial. It would be the DSMB's prerogative to consider all information made available to them in their decision to continue or stop the trial regardless of the above suggested statistical stopping guideline.

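### Stroke death is defined over the longer of 7 days and the hospital stay in Section 8.2 but monitored over the shorter in Section 8.8, and both windows depend on discharge

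*Protocol*

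**What the plan says.** Section 8.2 of the protocol, the list of formal definitions, describes stroke death as "Death from stroke (neurological death attributed to the stroke) within 7 days" (± 6 hours) "or during hospitalization for the qualifying stroke". Either limb is enough. The text does not say from what moment the 7 days run.

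Section 8.8 opens with "Incidences of the following specific adverse events are monitored by the Trial EC in a blinded manner" and adds that unblinded trial personnel and the DSMB follow the same events by treatment group. Its stroke-death item reads "Neurological death from stroke during hospitalization or within 7 days" (± 6 hours) "of randomization, whichever is shorter". Here the starting point is named, and the shorter of the two limbs applies.

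Two other places limit the reach of the point. Section 10.2.3 says "We propose to use the 30-day mortality as the primary safety outcome", and Section 10.7.2 says "The above stopping guideline is based on the total number of deaths observed within 30 days". Section 8.8 itself also lists death from any cause at 30 (± 7) and 90 (± 14) days.

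**The concern.** The two sections name one event, use the same two limbs, and combine them in opposite ways: a union in 8.2, an intersection in 8.8. Nothing else in the protocol reconciles them. A count built on the formal definition and a count built on the monitoring list can differ, and a report headed stroke death does not show which was used.

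The second problem is shared by both wordings. Discharge happens after randomization, so length of stay could be affected by treatment. Section 7.1 names volume overload as the major concern with albumin. If such a complication altered length of stay in one arm, the arms would be observed for stroke death over different periods. Stroke death is the only item in 8.8 whose window is tied to discharge; every other window there is a fixed number of hours or days.

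At stake is the clarity of the only cause-specific death item on the list that the DSMB sees by arm. Section 10.7.2 cites concerns about excess deaths in one group in Part 1, and asks the DSMB to weigh other pertinent data beside the mortality guideline.

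**Working it through.** The plan states no figure for this item, so the check is one of logic.

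**Notation.** Let L be the days from randomization to discharge from the index hospitalization (or to death, if the subject dies in hospital), and t the day of a neurological death attributed to the stroke. Take 8.2's unnamed starting point to be randomization, as in 8.8, and leave aside the ± 6 hours.

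- Section 8.2 counts the death if t ≤ 7 or if it occurs in hospital. The window is max(L, 7).
- Section 8.8 counts the death only within the shorter limb. The window is min(L, 7).

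**Cases.**

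| Neurological death | L | max(L, 7) | min(L, 7) | 8.2 | 8.8 |
|---|---|---|---|---|---|
| In hospital, day 5 | 5 | 7 | 5 | counted | counted |
| In hospital, day 12 | 12 | 12 | 7 | counted | not counted |
| Day 5, after discharge on day 3 | 3 | 7 | 3 | counted | not counted |
| Day 10, after discharge on day 3 | 3 | 7 | 3 | not counted | not counted |

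The sections disagree exactly when min(L, 7) < t ≤ max(L, 7). Because min(L, 7) never exceeds max(L, 7), the 8.8 count can never be higher than the 8.2 count.

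**Dependence on length of stay.** The 8.2 window grows with any stay beyond 7 days and has no upper limit. The 8.8 window shrinks with any stay under 7 days and is capped at 7. So under 8.8 a prolonged stay matters only for a subject who would otherwise have left before day 7 and who dies a neurological death by day 7. Under 8.2 it matters for neurological deaths after day 7.

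**Size.** The number of deaths with min(L, 7) < t ≤ max(L, 7) needs the distribution of stay and the neurological share of deaths by day. The protocol gives neither. The 165 deaths in the last row of Table 10.7.2 (0.15 × 1,100) are all-cause deaths within 30 days under an assumed rate. They are not even an upper bound, because 8.2 would also take in an in-hospital stroke death after day 30.

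**What does not change.** The primary safety outcome, its Cox analysis (Section 10.4.3) and the stopping guideline use all deaths within 30 days. None uses the stroke-death window.

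**The case against.** The best defence is that the sections do different jobs: 8.2 says what an event is, and 8.8 says over what period it is watched. Section 8.8 narrows other events in the same way. Section 8.2 treats any post-treatment atrial fibrillation as an adverse event, while 8.8 follows it for 48 (± 6) hours. Recurrent stroke has no upper time limit in 8.2, and 8.8 stops at 30 (± 7) days. Read alone, 8.8 gives one answer for the monitored count, and that answer matches the acute-phase visit in Section 6.1, held at day 7 or at discharge if earlier. So the shorter window may well be intended.

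Part of this stands. A programmer who used 8.8 only would have an unambiguous rule. But atrial fibrillation and recurrent stroke carry no competing end point in 8.2, whereas stroke death carries both limbs there, joined the other way. Where a window is given in both places for pulmonary edema and for symptomatic ICH, the two agree (48 and 24 hours). Nor need a visit schedule limit the ascertainment of deaths: Section 8.4 records serious events, which include any death, through 12 months.

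The point about consequence stands in full. The day-12 and the day-5 death both reach the DSMB by arm in the 30-day all-cause count. Only the cause-specific label is affected.

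It is also true that aligning the wording of the two sections, in either direction, would remove the contradiction. It would not remove the dependence on discharge.

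**Conclusion.** The inconsistency is real and small. Sections 8.2 and 8.8 give the same event opposite windows, and both windows depend on a post-randomization event. The effect is limited to a descriptive count of stroke deaths by arm; no test, boundary or sample size moves. The conclusion rests on the plain wording of the two sections and on taking randomization as the start of the 7 days in 8.2.

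Four stronger readings are not supported:

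- **That mortality monitoring is compromised.** It is not: all-cause death at 30 and 90 days is followed separately, and 30-day all-cause death drives the guideline.
- **That a known number of deaths is misclassified.** Any such number needs a share that the protocol does not give.
- **That the arms are in fact observed unequally.** The protocol does not show that stay differs by arm. This is a risk built into the definition, not an observed bias.
- **That Part 2 exists because of excess deaths.** Section 10.7.2 says only that those concerns led to the safety guidelines, and Section 10.4.3 mentions that Part 1 enrollment was suspended without giving a reason.

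**What to change.** Use one definition in both 8.2 and 8.8: neurological death attributed to the qualifying stroke within a fixed number of days from randomization, regardless of discharge. Seven days (± 6 hours) is an obvious candidate, since both sections already use it. Name randomization as the starting point in 8.2. List in-hospital stroke deaths after that window on a separate line, so that nothing captured by the present 8.2 wording is lost to the DSMB.

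The cost is a wording change and a matching change to the report program. Section 9 already requires the date and the underlying and contributing causes of each death, so no new data are needed. Reports already issued could be re-tabulated from the same records.

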9. CRITERIA FOR INTERVENTION DISCONTINUATION

There are only three ways that a randomized subject may prematurely discontinue participation in the Trial prior to completing the 12-month follow-up assessment: (1) the subject dies; (2) the subject withdraws consent; or (3) the subject becomes lost to follow-up (LTFU). Every study subject has the right to withdraw voluntarily from the study at any time for any reason without prejudice to his/her future medical care by the physician or at the institution. For the occasional participant who withdraws consent, the date and reason for consent withdrawal must be documented.

Since the assessments made at the 3-month follow-up visit provide the primary outcome measure for the Trial, the Study Coordinator, or designee, should start approximately one month prior to the target date for a subject's 3-month follow-up visit to try to make contact with the subject to schedule the 3-month follow-up visit. For the subject who fails to show up at the scheduled 3-month follow-up visit, all efforts should be made to contact the subject and reschedule the visit; and failing that, the Study Coordinator, or designee, should attempt to gather as much data as possible over the telephone. For the 1-, 6-, 9- and 12-month follow-up telephone contact, the Study Coordinator, or designee, must make at least five attempts over the course of two weeks. When all methods have been tried and have failed, the subject is coded as lost to follow-up in the End-of-Study CRF.

The procedure to be followed at the time of premature termination is: 1) to check for the development of adverse events; and 2) to complete the End-of-Study form with explanation of why the participant is withdrawing or has withdrawn. In case of death of a subject, additional data on the date and causes of death (underlying and contributing) must be collected.

10. STATISTICAL CONSIDERATIONS

10.1 Overview

The primary analysis for the Trial is to test the hypothesis of superiority of ALB therapy over placebo in acute ischemic stroke subjects, adjusting for the effects of thrombolysis and baseline stroke severity. The study is a parallel two-arm design with concurrent controls where eligible patients are randomized in 1:1 ratio to either the ALB group or the saline group. The primary outcome for efficacy/futility is the proportion of subjects within each group with favorable outcome as defined as mRS score of 0 or 1 and/or NIHSS score of 0 or 1 at 3 months from randomization. Interim analyses for overwhelming efficacy and futility as well as for safety are incorporated into the Trial.

10.2 Outcomes

10.2.1 Primary Efficacy Outcome

The primary outcome measure is the favorable outcome defined as either NIHSS score of 0 or 1 and/or mRS score of 0 or 1 at 3 months from randomization. Interim analyses for futility and efficacy are based on the proportion of subjects with the favorable outcome.

The choice of this outcome measure is due to the putative effect of ALB as a neuroprotective agent. The conventional outcome measure of clinical outcome for acute ischemic stroke treatment is the functional outcome as measured by the mRS at 3 months from randomization or baseline. We concur that any treatment for acute ischemic stroke should yield good functional outcome as measured by mRS score of 0 or 1 and sometimes 2. However, alternatively, if ALB therapy is an effective neuroprotective agent, we would expect to see good neurological outcome as measured by the NIHSS score of 0 or 1. Therefore, we selected the composite outcome where either the good functional or good neurological outcome would qualify as evidence of a beneficial ALB treatment effect.

10.2.2 Secondary Outcomes

The following are outcome measures to be evaluated as supportive evidence (or lack thereof) of the ALB treatment effect: (1) mRS score at 3 months; (2) mRS score at 12 months; (3) NIHSS score at 24 hours; (4) NIHSS score at 3 months; (5) BI score at 3 months; (6) EuroQol scores at 3 months; (7) EuroQol scores at 12 months; (8) SSQOL at 3 months; (9) stroke-free status as assessed by QVSFS at 12 months; (10) ASPECTS score by CT scan at 24 (\pm 6) hours; (11) proportion of subjects who do not have symptomatic ICH within 24 (\pm 6) hours; and (12) cognition as assessed by Trailmaking A and B at 3 months. The specific treatment of each of these outcome measures is detailed in the Statistical Analysis Plan.

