The Canadian Coordinating Center, which is located in the Department of Clinical Neurosciences at the University of Calgary / Foothills Medical Centre, is responsible for the coordination and oversight of the investigators and study coordinators at the Canadian sites regarding Canadian regulatory affairs. The Canadian Coordinating Center will also function as the central review site for all neuro-imaging and EKGs.

Medical Safety Monitors (MSMs)

The MSMs are experienced stroke neurologists not affiliated with any of the institutions participating in the ALIAS Trial. The MSMs' responsibilities are to review all SAEs and determine whether they are possibly related to the study drug administration, and to adjudicate adverse outcome events (e.g., recurrent stroke, MI, symptomatic ICH). Originally, the MSMs are blinded with regard to treatment assignment of SAE cases; however, if the DSMB requests that they be unblinded, their

communications, if any, with members of the ALIAS Executive Committee will be conducted to preserve the blinded nature of the Executive Committee members.

Data and Safety Monitoring Board (DSMB)

The Data and Safety Monitoring Board (DSMB) is appointed by the NINDS Director and managed by the NINDS Clinical Trials group. Its overarching responsibility is the oversight of safety of the Trial participants. They review reports on SAEs, request additional data/information, if necessary, and must be cognizant of external new information regarding the safety of ALB treatment. Upon review of periodic data, they advise the NINDS regarding continuation of the Trial.

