1.2 Secondary Objectives

Secondary aims are to compare ALB therapy to placebo with respect to the following:

- overall clinical outcome (as assessed by the global statistical test of NIHSS, mRS, and Barthel Index scores) at 3 months post-randomization.
- overall clinical outcome as assessed by the full scale of the modified Rankin scale.
- neurological outcome as assessed by NIHSS score at 3 months post-randomization.
- functional outcome as assessed by mRS and by Barthel Index at 3 months post randomization.
- quality-of-life as assessed by EuroQol at 3 months and 1 year post-randomization, and by Stroke-Specific Quality of Life (SSQOL) instruments at 3 months post-randomization.
- robustness of ALB therapy as measured by a favorable outcome of mRS of 0 or 1 at one year post-randomization.
- incidence of recurrent ischemic stroke within 1 month, 3 months and 1 year post-randomization, as assessed by Questionnaire to Validate Stroke-Free Status (QVSFS).
- incidence of symptomatic ICH within 24 (\pm 6) hours of randomization.
- mortality within 3 months and within 1 year post-randomization.
- cognition measured at 3 months by Trailmaking A and B.

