6.2.4 Post-Intervention Evaluations

Subjects are followed for 1 year (12 months) from randomization. At 3 months* (\pm 14 days) post-randomization, each subject is required to come to the clinic for the determination of clinical outcome of the qualifying stroke – NIHSS, mRS, and BI. Outcomes are determined by a clinical investigator (physician or study coordinator) at the site who is certified to administer NIHSS and mRS, **AND** who is blinded to the subject’s admission treatment assignment, acute in-hospital course, and imaging data.

Subjects are also followed by telephone contact at 1 month* (\pm 7 days), 6 months* (\pm 14 days), 9 months* (\pm 14 days), and 12 months* (\pm 14 days) post-randomization.

At all contacts, data are collected on the subject’s current vital status, medical status, living arrangement, occurrence of AEs and/or SAEs; and, a mRS assessment is performed. In addition, all subjects complete the EuroQol [1] at 3 months and 12 months, the Questionnaire to Validate a Stroke-Free Status (QVSFS) [52] at 3, 6, 9, and 12 months, the Stroke-Specific Quality of Life (SS-QOL) [113,114] instruments at 3 months, and Trailmaking A and B at 3 months [125,126,127].

All efforts should be made to ascertain at least the vital status of subjects who are lost to follow-up prior to his/her 12-month follow-up date.

[*In this Protocol, “3 months” shall be defined as 90 days; “1 month” as 30 days; “6 months” as 180 days; “9 months” as 270 days; and, “12 months” as 365 days.]

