6.2.5 Final Evaluations

At the 12-month anniversary date (\pm 14 days) of each subject’s randomization date, the study coordinator, or other designated personnel, contacts the subject via telephone to evaluate mRS, EuroQol, QVSFS, follow-up status, new SAEs and unresolved previously reported SAEs since the last contact, and to complete the end-of-study CRF. If a subject dies prior to that date, the end of study/death CRFs must be completed. The study coordinator, or other designated personnel, should get as much information as possible regarding the date, time, and circumstances of the subject’s death.

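### The QVSFS outcome cannot deliver the stated incidence of recurrent ischemic stroke: no questionnaire is given at 1 month or after death, and the objective, visit schedule and outcome list name different time points

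*Protocol*

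**What the plan says.** Protocol section 1.2 (and the Synopsis) sets as a secondary objective the "incidence of recurrent ischemic stroke within 1 month, 3 months and 1 year post-randomization, as assessed by Questionnaire to Validate Stroke-Free Status (QVSFS"). Section 10.2.2 reduces this to one item, "stroke-free status as assessed by QVSFS at 12 months", and leaves the specific treatment of each outcome to the SAP.

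Section 6.2.4 has subjects complete "the Questionnaire to Validate a Stroke-Free Status (QVSFS) [52] at 3, 6, 9, and 12 months", and the schedule in 6.1 agrees. Section 6.2.5 describes the last assessment: the coordinator "contacts the subject via telephone to evaluate mRS, EuroQol, QVSFS, follow-up status" and other items. For a death, the same section says "If a subject dies prior to that date, the end of study/death CRFs must be completed". No informant or proxy for the questionnaire is mentioned.

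Recurrent stroke is also captured by a separate route. Section 8.2 defines it clinically (new vascular territory, at least 48 hours after the first event). The Medical Safety Monitors (MSMs) are charged "to adjudicate adverse outcome events (e.g., recurrent stroke, MI, symptomatic ICH"). Section 8.4 states that "all serious AEs occurring through the 12-month follow-up visit are recorded", and 8.1 makes every death a serious event. Section 9 requires underlying and contributing causes of death. Section 8.8 monitors recurrent stroke within 30 days by treatment group.

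**The concern.** An incidence counts events in everyone at risk from randomization, including people who later die. A questionnaire completed by the subject at fixed contacts counts what subjects still alive and reachable report. The two differ most where deaths are early and frequent, as they are expected to be here.

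Early mortality is also where this trial has reason to expect a difference between arms. Section 10.2.3 makes 30-day death the primary safety outcome because the groups differed on it in Part 1. If that recurs, subjects with a questionnaire are a selected group after randomization. The arms could then differ on questionnaire status with no difference in recurrence, or the reverse.

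There is also a plain inconsistency. The objective names three time points, the schedule omits the first, and the outcome list keeps only the last.

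**Working it through.** **1. Time points side by side**

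| Place | What is named | When |
|---|---|---|
| Synopsis, 1.2 | Incidence of recurrent ischemic stroke, by QVSFS | 1, 3 and 12 months |
| 6.1, 6.2.4 | QVSFS given | 3, 6, 9 and 12 months |
| 10.2.2 | QVSFS stroke-free status | 12 months only |
| 8.8 | Recurrent stroke as a monitored event, by group | 30 (±7) days |

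The 1-month component has no 1-month questionnaire. A 3-month questionnaire could reveal a first-month recurrence in a survivor, but the protocol does not say that it is used to date events.

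**2. The protocol's own figure.** Table 10.7.2 assumes a 15% 30-day death rate. Expected deaths = N × 0.15. For N = 100, 200, 600 and 1,100 this gives 15, 30, 90 and 165, matching the table.

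**3. Who can have a questionnaire**

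- Dead by day 30, before any QVSFS: 1,100 × 0.15 = 165, leaving at most 1,100 − 165 = 935.
- If 5% more are lost by month 3 (section 10.6 expects less than 5%): 1,100 × 0.05 = 55, so 165 + 55 = 220 (20%) have none and 880 remain.
- If 30-day mortality were 10% or 20% (assumption), deaths would be 110 or 220.
- Deaths between day 30 and month 3 add to these counts. Deaths after month 3 remove the 12-month questionnaire.

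**4. Whether imputation recovers the events.** Section 10.6 applies methods similar to those for the primary outcome to binary secondary outcomes.

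- *Carrying the last value forward.* A subject stroke-free at month 6 who dies of a recurrence at month 8 stays stroke-free. A subject dead by day 30 has no value to carry.
- *Scoring death as the bad outcome.* The outcome becomes recurrence or death. As an illustration, assume 5% recurrence, 20% of it fatal, and the fatal ones among the 165 deaths. Recurrences = 55, fatal = 11, and the share not stroke-free = (55 − 11 + 165) / 1,100 = 209 / 1,100 = 19%, against a true 5%. With assumed recurrence of 3–10% and a fatal share of 10–40%, the figure runs from about 17% to 24%.

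**5. Possible effect on the comparison (illustration).** Suppose both arms have the same true recurrence and only non-fatal recurrences are counted. The ratio of counts is (1 − fatal share in one arm) / (1 − fatal share in the other). Assumed shares of 40% and 20% give 0.60 / 0.80 = 0.75; 30% and 20% give 0.70 / 0.80 = 0.875. Swapping the arms reverses the direction.

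**6. What the protocol cannot tell us.** It gives neither a recurrence rate nor a fatal share. Under the assumed ranges in step 4, fatal recurrences would number from 33 × 0.10 ≈ 3 to 110 × 0.40 = 44. That width shows that the count is unknown.

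**The case against.** **Treatment is left to the SAP.** Section 10.2.2 says so, and the SAP may state how deaths are classified or that adverse-event data feed in. This stands for the handling of deaths. It does not cure the instrument and time points, which the protocol itself fixes inconsistently.

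**Nothing says that the dead are excluded.** A reader might infer a survivors-only analysis in which fatal recurrences disappear. The document does not support that. Section 10.5 analyzes the efficacy outcomes by intention to treat and 10.6 imputes missing values, so subjects who die may well stay in the denominator. The narrower point remains: a recurrence in a subject who dies before the next questionnaire is not counted by it as a recurrence.

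**The events are recorded.** This is correct. Fatal recurrences reach the database through serious-event reports and causes of death, and first-month recurrence is compared by group under 8.8. The gap is that the named outcome does not draw on these sources.

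**The adverse-event record is not a complete substitute.** Non-serious events are collected only to 3 months (8.4), so a later non-serious recurrence could be found by the QVSFS and missed by an endpoint built on serious events alone. The 8.2 definition does not distinguish ischemic from hemorrhagic stroke. Both objections stand, and the fix has to meet them.

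**The consequence is limited.** This is one of twelve supportive outcomes, tested at two-sided 0.01 (10.4.2), and effectiveness rests solely on the primary outcome (10.4.4). That is also correct.

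**Conclusion.** The point holds as a mismatch between objective and measure. No questionnaire is given at 1 month, only 12-month status is listed as an outcome, and about 165 of 1,100 subjects (15%, on the protocol's mortality assumption) never have one. As written, the QVSFS outcome cannot deliver the incidence in the objective, and the stated imputation changes the question or misses later fatal events.

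A reader might go further and put a percentage on the recurrences missed. The protocol does not allow it, because every such figure needs an assumed recurrence rate and fatal share. A biased comparison is likewise possible if early mortality differs by arm, but it is not demonstrated. The conclusion assumes that the questionnaire needs a living respondent; the protocol neither provides for nor forbids a proxy. The change should be made, but the primary analysis does not depend on it.

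**What to change.** Reconcile the Synopsis and sections 1.2, 6.2.4 and 10.2.2 around one outcome:

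- **Event:** first recurrent ischemic stroke under the 8.2 definition, adjudicated by the MSMs, with stroke type recorded at adjudication.
- **Sources:** adverse-event, serious-event and death records, plus any event prompted by the QVSFS at each contact where it is given. The last source captures non-serious recurrences after month 3.
- **Analysis:** cumulative incidence at 1, 3 and 12 months by arm, with death as a competing event.
- **Supportive:** questionnaire stroke-free status, labelled as describing survivors.

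The cost is a change of wording, one extra analysis, and a stroke-type field with a short adjudication step for events that reach the MSMs through the questionnaire rather than a serious-event report. No new subject contact is needed, because adverse events are already collected at every contact, including month 1.
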